### **4.4 Early Withdrawal of Subjects**

Subjects may choose to withdraw from the study at any time, for any reason without penalty or loss of benefit.

Due to the short duration of the subject participation in the study, there is only one (1) foreseeable scenario in which a subject could withdraw prior to completion of the study:

- A subject might withdraw from the subject if use of the device(s) is uncomfortable. Some patients could be claustrophobic and find the treatment uncomfortable.

For any subject that withdraws prior to completion of the study for this reason, the data will be omitted from the final analysis. The subject may be replaced with another subject to ensure that the full sample size is obtained.

Abrupt termination of study treatment is not expected to affect subject safety, therefore no transition procedures are required.

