### **3.2 Primary/Secondary Endpoints**

The following primary and secondary endpoints are to be analyzed in the study:

Primary endpoints:

1. Difference in spirometry measurements (FEV1, FVC, PEF, FEF25-75% and TV) between the AffloVest device and Monarch devices.

Secondary endpoints:

1. Survey results using a Likert scale related to:
  - a. Subject opinion on using each device on a daily basis
  - b. Subject opinion on lifestyle fit for each device
  - c. Subject opinion on lifestyle obtrusiveness of each device
  - d. Subject opinion on mobility during use of each device
  - e. Subject opinion on noise level of each device
  - f. Subject opinion on compliance with treatment of each device

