## **4 Subject Selection and Withdrawal**

### **4.1 Inclusion Criteria**

The following subjects shall be eligible for study enrollment:

1. Healthy subject, ages 18 – 50

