### **4.2 Exclusion Criteria**

The following subjects shall be ineligible for study enrollment:

1. Non-ambulatory
2. Diagnosed neuromuscular disorder
3. Currently using any type of oscillation vest therapy
4. Diagnosed co-morbid condition (i.e. lung cancer, other lung disorder or disease)
5. Currently enrolled in a medical research study
6. Non-English speaking
7. Presence of the following active implantable devices:
  - a. Pacemakers
  - b. Neurostimulators
  - c. Infusion pumps
  - d. Circulatory support devices
  - e. Implantable cardioverter defibrillators (ICD's)
  - f. Cochlear implants
8. Head and/or neck injury that has not yet been stabilized.
9. Active hemorrhage with hemodynamic instability

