### 5.2 Treatment/Dosing Regimen

Each subject shall perform the following regimen:

1. Pre-baseline spirometry measurements (without device on patient)
2. Placement of either AffloVest or Monarch on subject, turn device ON, allow subject to acclimate to device for five (5) minutes
  - a. Repeat spirometry measurements
3. Remove device from subject and allow subject to recover for fifteen (15) minutes
4. Interim-baseline spirometry measurements (without device on patient)
5. Placement of other product (either AffloVest or Monarch, whichever was not used previously) on subject, turn device ON, allow subject to acclimate to device for five (5) minutes
  - a. Repeat spirometry measurements
6. Remove device from subject and allow subject to recover for fifteen (15) minutes
7. Post-baseline spirometry measurements (without device on patient)

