### **7.3 Subject Population(s) for Analysis**

All eligible subjects shall be included in the analysis.

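### Section 4.4 drops all data from subjects who leave because a vest is uncomfortable; with a survey given only at the end of the visit, device intolerance can go unseen in the report

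*Combined protocol and SAP*

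**What the plan says.** - **Withdrawal (4.4).** Subjects may leave at any time for any reason, but the section holds that "there is only one (1) foreseeable scenario in which a subject could withdraw prior to completion of the study", namely discomfort with a device, with claustrophobia as the example. The data rule is: "For any subject that withdraws prior to completion of the study for this reason, the data will be omitted from the final analysis". Such a subject may be replaced. Nothing is said about data from subjects who leave for another reason, or about the device order of a replacement.
- **Analysis population (7.3).** "All eligible subjects shall be included in the analysis". Eligibility is defined only by the enrolment criteria in 4.1 and 4.2. Sections 7.3 and 4.4 do not refer to each other.
- **Endpoints (3.2).** The primary endpoint is "Difference in spirometry measurements (FEV1, FVC, PEF, FEF25-75% and TV) between the AffloVest device and Monarch devices". The secondary endpoints are Likert opinions of each device, for example "Subject opinion on using each device on a daily basis", together with lifestyle fit, obtrusiveness, mobility, noise and compliance.
- **Survey timing (3.1; Section 6, Phase 3).** The survey comes at the end of the visit, after all spirometry. No survey at withdrawal is described.
- **Analysis (7.2).** Each subject's baseline is the mean of the pre-, interim- and post-baseline readings. It is compared with the reading on each device by a t-test.

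**The concern.** The exclusion is triggered by a reason that the device itself causes, not by missing data. Someone who cannot tolerate a vest may plausibly rate it low on daily use, lifestyle fit, obtrusiveness or compliance, so the secondary endpoints are where the selection matters most. The opinions of an early leaver are lost twice: the survey has not yet been given, and 4.4 would discard it if it had.

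Replacement then restores the count to 10. Section 4.4 does not ask for withdrawals to be counted by device, and 9.2 names only the spirometry data and the survey as source documents. Section 8.2 requires observed or volunteered adverse events to be reported, but 8.1 defines an adverse event by reference to death, serious injury or malfunction, so plain discomfort need not appear there either. A reader of the results could therefore miss that a vest drove someone out of the study.

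**Working it through.** The plan gives no withdrawal rate, SD or power, so there is no stated figure to reproduce. The check follows the visit and counts what is lost at each exit point.

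**1. What a leaver holds.** Step numbers are from 5.2; the fitting step is from Section 6, Phase 2.

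| Subject leaves | Readings held (of 5) | Device readings | All three baselines? | Complete device pair? |
|---|---|---|---|---|
| At fitting, before any spirometry | 0 | 0 | no | no |
| After step 1, before 2a | 1 | 0 | no | no |
| After 2a, before step 4 | 2 | 1 | no | no |
| After step 4, before 5a | 3 | 1 | no | no |
| After 5a, before step 7 | 4 | 2 | no | yes |
| After step 7, before the survey | 5 | 2 | yes | yes |

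The 7.2 comparison needs all three baselines, so 4.4 removes a planned device-versus-baseline result only in the last row. The 3.2 contrast needs both device readings but no baseline, because with a common baseline B, (A − B) − (M − B) = A − M. A usable pair is therefore lost only in the last two rows. By then both vests have given their readings, and the subject is at or past the second instance of "Remove device from subject and allow subject to recover for fifteen (15) minutes". That is not when discomfort is most likely to make someone leave.

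**2. Precision, one complete pair lost and not replaced.** Paired 95% half-width in SD units = t(0.975, n − 1)/√n.
- n = 10: 0.7154
- n = 9: 0.7687
- Ratio: 0.7687/0.7154 = 1.0745, about 7% wider at equal SD

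If the subject is replaced, n stays at 10 and there is no widening.

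**3. Chance of at least one withdrawal in 10.** The rate d is an assumption; P = 1 − (1 − d)^10.
- d = 5%: 0.401
- d = 10%: 0.651
- d = 20%: 0.893

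**4. Survey, illustration only.** Assume a 5-point scale, 10 completers with mean 4 for a device, and one replaced withdrawer who would have scored it s. The mean over all 11 is (40 + s)/11, so the completers' mean is higher by 4 − (40 + s)/11 = (4 − s)/11.
- s = 1: 3/11 = 0.27
- s = 2: 2/11 = 0.18

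This is the joint effect of omission and survey timing. With the timing as written there is no survey to omit, so 4.4 alone contributes none of it.

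**5. Order balance.** The list in 5.3 covers subjects 1 to 10 only. If a replacement simply became subject 11 under the same alternation, it would take AffloVest first. Losing an odd-numbered subject then leaves 5:5 and losing an even-numbered one leaves 6:4, each half the time if any subject is equally likely to leave.

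**6. Why a shortened baseline is not a free repair.** Counting only the 5-minute acclimation and 15-minute recovery periods, the baselines fall at 0, 20 and 40 minutes, with centre 20. Without the last one the centre is 10. Under a time trend that subject's contrasts would not be comparable with the others.

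**The case against.** The strongest reply is that the quoted sentence does little harm by itself. Section 7.2 already makes spirometry unusable for a device-versus-baseline test in anyone who leaves before step 7, and a subject who leaves at fitting has no readings to lose. The survey loss comes mainly from the end-of-visit timing. The 7% needs a lost pair that is not replaced, and 4.4 permits replacement. Comfort is not a survey item, and noise has no evident link with it. All of this stands, and it confines the point largely to acceptability and to the visibility of withdrawals.

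A reader might infer that 4.4 and 7.3 flatly contradict each other, since a subject who withdraws is still eligible under 4.1 and 4.2. The documents do not compel that. Section 4.4 can be read as a specific exception to a one-line general rule, which leaves a missing cross-reference.

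A reader might also infer that the survey is biased in favour of one vest. That is plausible for a subject driven out by one vest, but a subject who dislikes both could leave the contrast largely unchanged, and the documents give nothing from which to derive a direction.

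What the reply does not remove is that 4.4 is an active rule that excludes by a device-related reason and permits replacement, with no requirement to show that it happened.

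**Conclusion.** The point holds as a cheap improvement of minor to moderate weight. Section 4.4 and the survey timing together restrict the acceptability results to subjects who tolerated both vests, and can leave intolerance invisible. The effect is zero without withdrawals. The shift of 0.18 to 0.27 on a survey item rests wholly on the assumed scale, mean and withdrawer score, and the withdrawal probabilities rest on assumed rates.

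The documents do not support reading this as a material threat to the primary spirometry result. A complete pair is lost only after step 5a and a planned baseline comparison only after step 7. The precision cost is about 7% for one unreplaced pair of 10. The rules are still best settled before data are seen, because the study is unblinded and a decision made afterwards would itself allow selection.

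**What to change.** - **4.4:** replace the omission sentence with: 'Data collected up to withdrawal are retained; each comparison uses all subjects with the readings it needs; the number of withdrawals and the reasons are reported by device and period beside the survey results; a withdrawing subject is invited, but not required, to complete the survey for each device worn; a replacement takes the device order of the subject replaced, and a withdrawn subject with both device readings is kept in the paired comparison and is not replaced for it.' The last clause prevents a withdrawer and a replacement from both counting, which would give 11 pairs split 6:5.
- **3.1 and Section 6, Phase 3:** add 'or at withdrawal, if the subject agrees' to the survey timing. This and the 4.4 change are both needed; neither alone brings an early leaver's opinions into the analysis.
- **7.3:** refer to 4.4.
- **7.2:** state the paired within-subject AffloVest–Monarch difference as the analysis of the 3.2 primary endpoint, which 7.2 does not now test directly. Keep the three-reading baseline for the device-versus-baseline comparisons.

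Cost: wording in five places and the offer of an existing short survey at exit, with no added visits or measurements. Denominators may differ between analyses, and acceptability may look slightly less favourable. A subject who wore only one device still cannot enter the between-device comparison; the withdrawal count makes that selection visible but does not remove it.

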## **5 Investigational Product**

### 5.1 Description

AffloVest Oscillation Vest - The product is a home-use device and appears as a wearable vest with accessories (i.e. battery, A/C power supply, etc.)

Hill-Rom Monarch – The product is a home-use device and appears as a wearable vest with accessories (i.e. battery, A/C power supply, etc.)

### 5.2 Treatment/Dosing Regimen

Each subject shall perform the following regimen:

1. Pre-baseline spirometry measurements (without device on patient)
2. Placement of either AffloVest or Monarch on subject, turn device ON, allow subject to acclimate to device for five (5) minutes
  - a. Repeat spirometry measurements
3. Remove device from subject and allow subject to recover for fifteen (15) minutes
4. Interim-baseline spirometry measurements (without device on patient)
5. Placement of other product (either AffloVest or Monarch, whichever was not used previously) on subject, turn device ON, allow subject to acclimate to device for five (5) minutes
  - a. Repeat spirometry measurements
6. Remove device from subject and allow subject to recover for fifteen (15) minutes
7. Post-baseline spirometry measurements (without device on patient)

### 5.3 Method for Assigning Subjects to Treatment/Dosing Groups

Subjects shall be assigned according to the following in order of study enrollment. This approach shall control for any effect from which device is used first by alternating the device order.

Subject Number	First Device	Second Device
1	AffloVest	Monarch
2	Monarch	AffloVest
3	AffloVest	Monarch
4	Monarch	AffloVest
5	AffloVest	Monarch
6	Monarch	AffloVest
7	AffloVest	Monarch
8	Monarch	AffloVest
9	AffloVest	Monarch
10	Monarch	AffloVest

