## STUDY SUMMARY

Title	AffloVest Comparative Study for Air Flow in the Lungs
Protocol Number	2018-02
Phase	Device, Phase I
Methodology	
The study will be broken into one (1) arm:
 
 
- AffloVest® & Monarch™
 
 
Within each arm, the order of products will be also randomized.
 
Baseline spirometry (FEV1, FVC, PEF, FEF25-75% and TV) will be taken at the beginning, middle and end of each subject trial without any device on the subject.
 
A product (AffloVest or Monarch vest) will be placed onto subject and turned ON to the highest frequency and intensity settings, then the subject will be given a certain period. The spirometry measurements will then be repeated. The product will be removed and the subject allowed a recovery period, then the other product will be placed on the subject, turned ON and spirometry measurements repeated. A short questionnaire will also be included.

Study Duration	Approximately one (1) month
Study Center(s)	Pulmonary Disease Specialists, PA (d/b/a PDS Research) [name]
Objectives	Investigate impact of high-frequency chest wall oscillation therapy on spirometry values (FEV1, FVC, PEF, FEF25-75% and TV) during use of different products and comparing to baseline values to determine any significant variation in air flow in the lungs.
Number of subjects	10
Main Inclusion and Exclusion Criteria	
Inclusion: Healthy subject, ages 18 – 50
 
Exclusion: Non-ambulatory, diagnosed neuromuscular disorder, currently using any type of oscillation vest therapy, diagnosed co-morbid condition (i.e. lung cancer, other lung disorder or disease), currently enrolled in a medical research study, non-English speaking, presence of the following active implantable devices: pacemakers, neurostimulators, infusion pumps, circulatory support devices, implantable cardioverter defibrillators (ICD's), cochlear implants, presence of head and/or neck injury that has not yet been stabilized, presence of active hemorrhage with hemodynamic instability

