## **3 Study Design**

### **3.1 General Design**

This pilot study has been designed as follows:

- One (1) arm
- This is a pilot investigational study, based on the study design there are no blinding or randomization measures taken. It is expected that the degree of bias shall be low based on the subjective endpoints under study. Each subject shall serve as their own control as

baseline spirometry measurements will be performed at the beginning and end of the visit.

- Each subject will participate for a period of approximately two (2) hours.
- There is no subject follow-up, all measurements will be performed within the initial subject visit. At the end of the visit, each subject shall be required to complete a brief survey regarding their experience.

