### 2. Phase 2 – Initial Spirometry measurements

- After subject enrollment, the subject will be fitted with both an AffloVest product and Monarch vest
- An initial spirometry baseline will be taken using standard spirometry equipment and according to standard spirometry procedures, without any device on the subject.
- Depending on the subject enrollment number, the appropriate product will be placed onto the subject.
- The device will be turned on to the maximum frequency and intensity settings.
- The subject will be allowed five (5) minutes to acclimate to the device.
- The spirometry measurements will then be repeated in the same manner as above
- The device will be turned OFF and removed, and the subject will be allowed fifteen (15) minutes recovery
- An interim spirometry baseline will be taken using standard spirometry equipment and according to standard spirometry procedures, without any device on the subject.
- Depending on the subject enrollment number, the second appropriate product will be placed onto the subject.
- The device will be turned on to the maximum frequency and intensity settings.
- The subject will be allowed five (5) minutes to acclimate to the device.
- The spirometry measurements will then be repeated in the same manner as above
- The device will be turned OFF and removed, and the subject will be allowed fifteen (15) minutes recovery
- A final spirometry baseline will be taken using standard spirometry equipment and according to standard spirometry procedures, without any device on the subject

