### **7.2 Statistical Methods**

The metrics for the study shall be calculated as follows:

- Subject baseline values: An average of the pre-baseline, interim-baseline and post-baseline measurements shall be taken for FEV1, FVC, PEF, FEF25-75% and TV for each subject
- Comparison of the subject baseline values will be made with their values while using each device. A Student's t-test will be used to look for statistically significant differences at the 95% confidence level

Any deviation(s) from the original statistical plan shall be communicated to the IRB and the protocol shall be revised, if required.

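### Device order is controlled only by 5:5 alternation; the 7.2 t-test ignores sequence and period, which costs precision at 5:5 and lets a period effect shift the estimate if balance is lost (optional, low)

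*Combined protocol and SAP*

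**What the plan says.** - **Order.** Section 5.3 lists ten subjects. Odd numbers use AffloVest first and even numbers use Monarch first, five of each, and the list stops at 10. Its stated purpose: "This approach shall control for any effect from which device is used first by alternating the device order". Section 6, Phase 2, follows the same rule: "Depending on the subject enrollment number, the appropriate product will be placed onto the subject".
- **Analysis.** Section 7.2 averages the pre-, interim- and post-baseline readings, then states: "Comparison of the subject baseline values will be made with their values while using each device". The method is a Student's test: "t-test will be used to look for statistically significant differences at the 95% confidence level". No sequence or period term is mentioned, and the paired or unpaired form is not stated. The primary endpoint in 3.2 is the difference between the two devices.
- **Withdrawal.** For a subject who leaves because of discomfort, 4.4 says "the data will be omitted from the final analysis", and then: "The subject may be replaced with another subject to ensure that the full sample size is obtained". It gives the replacement neither a subject number nor a sequence.
- **Wording on randomisation.** The Study Summary says: "Within each arm, the order of products will be also randomized". Section 3.1 says "based on the study design there are no blinding or randomization measures taken", and 8.4 likewise says there is none.

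**The concern.** The protocol itself names device order as something to control. An order effect is plausible: each subject gives five sets of spirometry in one visit, with 15-minute recoveries (5.2), so practice or fatigue could move the second device's readings relative to the first. The design collects what is needed to remove such an effect, namely two sequence groups, but the analysis does not use it.

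Two consequences follow. While the groups are equal, a period effect inflates the error variance. If they become unequal, part of the period effect passes into the estimated device difference. Section 4.4 protects the total number of subjects but says nothing about balance between sequences.

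Separately, a report written from the Study Summary would claim a randomisation that did not take place.

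**Working it through.** **Inputs.** From the documents: n = 10, split 5:5 (5.3); 95% confidence level (7.2), taken as two-sided 5%; baselines before, between and after the devices (5.2). Section 7.1 says that no calculation lies behind n = 10, so there is no power figure to reproduce. Assumed, because the documents give neither: period effects π of 0 to 1.0, in units of the within-subject SD of D = AffloVest − Monarch, and a true difference δ of 1 such SD.

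**Model.** With π the second-period value minus the first, D has mean δ − π in AffloVest-first subjects and δ + π in Monarch-first subjects, with SD 1.

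**Bias of the unadjusted mean.** Absolute bias = π × |n₁ − n₂| / (n₁ + n₂).
- 5:5: 0.
- 5:4 or 4:5: π × 1/9 = 0.11π, so 0.03, 0.06 and 0.11 SD at π = 0.25, 0.5 and 1.0.
- 6:4: π × 2/10 = 0.20π, so 0.05, 0.10 and 0.20 SD.
- 7:3: π × 4/10 = 0.40π.

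The mean of the two sequence means, which is the period-adjusted estimate, has bias 0 at every split. For scale, the SE at n = 10 is 1/√10 = 0.32 SD, so the 6:4 bias at π = 0.25 is 0.05/0.32 = 0.16 SE.

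**How balance could be lost under 4.4.** One discomfort withdrawal without replacement gives 5:4 or 4:5. A replacement in the vacated row keeps 5:5. If the list were extended so that row 11 is AffloVest first, and that subject replaced a Monarch-first subject, the split would be 6:4. On the same extension, 7:3 needs three Monarch-first withdrawals: 5 + 2 against 2 + 1.

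**Precision at 5:5, device versus device.** Ignoring sequence, the expected variance of D is 1 + π² × 10/9, so the SD is 1.03, 1.13 and 1.45 at π = 0.25, 0.5 and 1.0. Simulated power, paired t-test at δ = 1:

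| π (SD) | Unadjusted (9 df) | With period term (8 df) |
|---|---|---|
| 0 | 80% | 79% |
| 0.25 | 78% | 79% |
| 0.5 | 72% | 79% |
| 1.0 | 48% | 79% |

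Exact noncentral t at π = 0 gives 0.803 and 0.791. Break-even is at about π = 0.2.

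**Precision at 5:5, device versus averaged baseline (the 7.2 contrast).** Assume a paired test, equal independent errors of variance 0.5 per reading, and linear drift. The contrast SD is √(0.5 × 4/3) = 0.816. Baselines fall at visit positions 1, 3 and 5 (mean 3) and devices at 2 and 4, so the shift is π/2, half that for device versus device, and any bias from imbalance is halved too. SE inflation = √(1 + (π/2)² × (10/9) / 0.667) = 1.01, 1.05 and 1.19 at π = 0.25, 0.5 and 1.0. Simulated power at a true difference of 1 SD of D is 93/93/91/86% at π = 0/0.25/0.5/1.0, against 92% with a period term.

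**Type I error of the unadjusted device-versus-device test** (simulated; the third decimal carries noise):

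| Split | π = 0.25 | π = 0.5 | π = 1.0 |
|---|---|---|---|
| 5:5 | 0.044 | 0.030 | 0.007 |
| 5:4 | 0.045 | 0.032 | 0.010 |
| 6:4 | 0.046 | 0.038 | 0.017 |
| 7:3 | 0.054 | 0.061 | 0.064 |

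The period-adjusted test stays at about 0.05 throughout.

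**Wording.** Sections 5.3 and 6 assign order by enrolment number; 3.1 and 8.4 deny randomisation. The Study Summary sentence stands alone against all four.

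**The case against.** The case for leaving the plan alone is substantial. Counterbalancing by design and then using a simple test is a recognised choice for a ten-subject pilot, and at 5:5 it does what 5.3 says for the mean. The large power losses belong to a device-versus-device test that 7.2 does not contain. For the contrast that 7.2 does describe, a period term loses slightly up to 0.25 SD and gains only about 1 point at 0.5 SD. Nothing in the documents shows that a larger drift is likely. Bias needs a withdrawal from a visit of about two hours by healthy subjects, a replacement that is missing or off sequence, and a real period effect. Finally, part of the proposed analysis repairs a separate mismatch, since 3.2 compares the devices and 7.2 compares each with baseline; that mismatch should not lend weight to this point.

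All of this stands, and it sets the low rating. It does not remove the point, because the better analysis uses groups already assigned and costs one degree of freedom.

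Three stronger readings are tempting, and the documents do not support them:
- *The planned comparison is biased or produces false positives.* Not at 5:5, where bias from an additive period effect is zero and the test is conservative. Error is still below 5% at 5:4 and 6:4. The exception is a remote 7:3, at about 0.06 for period effects of 0.5 to 1.0 SD.
- *Section 4.4 leads to a 6:4 split.* The 5.3 list has no row 11, and replacing a subject can equally be read as filling the vacated row. The rule is silent on sequence; it does not prescribe imbalance.
- *It is unclear whether order is randomised.* The 5.3 table settles conduct. The Study Summary sentence is a wording error.

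**Conclusion.** The point holds as an optional, low-severity improvement. At the planned split the cost of ignoring sequence and period is precision only: appreciable for a direct device comparison if the period effect reaches about half an SD, and small for the contrast now in 7.2. If balance is lost, the estimate shifts by a modest fraction of the period effect. These sizes rest on assumed period effects, a true difference of 1 SD, an additive period effect and, for the baseline contrast, pairing, equal independent errors and linear drift. None of these can be checked from the documents. Differential carryover is a separate matter, which neither alternation nor a period term resolves.

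**What to change.** In 7.2, analyse the within-subject AffloVest-minus-Monarch difference, the 3.2 endpoint, with a period term: a two-sequence crossover t-test, with 8 df at n = 10. If there is no period effect, the cost in power is about 1 point at 5:5 (80% to 79%), 2 at 5:4 (75% to 72–73%) and 3 at 6:4 (80% to 77–78%). No extra subjects or visits are needed.

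Two minor wording edits go with it:
- In 4.4 and 5.3, state that a replacement takes the sequence of the subject replaced.
- In the Study Summary, describe the order as alternated by enrolment number, in line with 5.3 and 6 (assignment by number) and with 3.1 and 8.4 (no randomisation).
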